4.0 Test Schedule

Tests and procedures	Screening Phase		Active Monitoring Phase				
	≤28 days prior to randomization	≤7 days prior to randomization	Baseline (Prior to Cycle 1 Day 1 treatment)	Day 15 of each cycle ⁸ (± 3 days)	Prior to dosing on Day 1 of ≥ cy 2 (± 3 days)	Prior to dosing at restaging (C3 and every other cycle after)	End of Tx (within 30 days after last dose of study drug)
History and exam, wt, ECOG PS	X			X	X		X
Height	X						
Adverse event assessment	X			X ¹	X ¹		X
CBC/ differential: WBC, hemoglobin, hematocrit, platelets, neutrophil count, lymphocyte count, monocyte count, eosinophil count		X	X ¹¹	X	X		X
Chemistry: Sodium, potassium, chloride, CO ₂ , BUN, creatinine, glucose, calcium, SGOT (AST), SGPT (ALT), total bilirubin, alk phos, albumin, total protein		X	X ¹¹	X	X		X
Magnesium		X		X ⁵	X ⁵		X ⁵
Tumor Blood Bio-Markers (CEA)		X			X (C2 only)	X (at each restaging)	
Serum Pregnancy test ²		X	X ¹¹			X	
Tumor measurement (CT or MRI of the chest, abdomen and pelvis) ³	X					X	
COLOMATE Companion Trial Recommendation Form ¹²	X						
Mandatory blood sample – whole blood ^{4, 9,R}			X				
Mandatory blood sample – plasma ^{4,9,R}			X		X (C2 only)	X (at each restaging)	X
Mandatory tissue sample– archival tumor paraffin ^{6,R}			X				

Tests and procedures	Screening Phase		Active Monitoring Phase				
	≤28 days prior to randomization	≤7 days prior to randomization	Baseline (Prior to Cycle 1 Day 1 treatment)	Day 15 of each cycle ⁸ (± 3 days)	Prior to dosing on Day 1 of ≥ cy 2 (± 3 days)	Prior to dosing at restaging (C3 and every other cycle after)	End of Tx (within 30 days after last dose of study drug)
Mandatory Patient Questionnaire Booklet (Appendix II) ¹⁰			X		X		X
Patient Medication Diary (Appendix IV) ¹³					X	X	X
Optional Blood sample-cfDNA Guardant 360 ^{4,7,R}							X

- 1 The adverse event assessment will be evaluated at the end of each cycle prior to the beginning of the next cycle and at day 15 visit for the first 6 cycles. Please note: only the maximum grade will be needed for data entry.
- 2 For women of childbearing potential only. Must be done ≤ 7 days prior to randomization.
- 3 Use same imaging throughout the study.
- 4 Kits are required for this collection. Refer to Section 14.0.
- 5 Only for patients receiving panitumumab.

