	Grade 4	Hold until resolution of fever and neutropenia to grade ≤ 1 , then resume at two dose levels lower. Discontinue after second occurrence.
	Diarrhea	
	Grade 1	Maintain current dose
	Grade 2	Hold until recovery to grade ≤ 1 , then resume at one dose level lower.
	Grade 3	1 st or 2 nd occurrence: Hold until recovery to grade ≤ 1 , then resume at one dose level lower. 3 rd occurrence: Discontinue
	Grade 4	1 st occurrence: Discontinue or hold until recovery to grade ≤ 1 , then resume at two dose levels lower. 2 nd occurrence: Discontinue
	Mucositis oral	
	Grade 1	Maintain current dose
	Grade 2	Hold until recovery to grade ≤ 1 , then resume at one dose level lower.
	Grade 3	1 st or 2 nd occurrence: Hold until recovery to grade ≤ 1 , then resume at one dose level lower. 3 rd occurrence: Discontinue
	Grade 4	1 st occurrence: Discontinue or hold until recovery to grade ≤ 1 , then resume at two dose levels lower. 2 nd occurrence: Discontinue
	Small intestinal or colonic obstruction	
	Grade 2	Hold regorafenib for partial obstruction requiring medical intervention. Resume all study drugs at current dose when obstruction is resolved to grade ≤ 1 .
	Grade 3 or 4	Hold for all study drugs for complete obstruction. If surgery is necessary, subject may resume all study drugs at current doses after full recovery from surgery with permission of Principal Investigator.
General disorders and administration site conditions	Fatigue	
	Grade 1	Maintain current dose
	Grade 2	Hold until recovery to grade ≤ 1 , then resume at one dose level lower.

→ → Use the NCI Common Terminology Criteria for Adverse Events (CTCAE) version 5.0* unless otherwise specified ← ←

CTCAE System/Organ/Class (SOC)	ADVERSE EVENT	ACTION**
	Grade 3	1 st or 2 nd occurrence: Hold until recovery to grade ≤ 1, then resume at one dose level lower. 3 rd occurrence: Discontinue
	Grade 4	1 st occurrence: Discontinue or hold until recovery to grade ≤ 1, then resume at two dose levels lower. 2 nd occurrence: Discontinue

^a Discontinue regorafenib for the following:

- Any occurrence of AST or ALT more than 20 times the upper limit of normal (ULN).
- Any occurrence of AST or ALT more than 3 times ULN with concurrent bilirubin more than 2 times ULN.
- Re-occurrence of AST or ALT more than 5 times ULN despite dose reduction.

* Located at [REDACTED]

** Use the following to describe actions in the Action column:

- Omit = Treatment is not given for this cycle

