10.0 Adverse Event (AE) Reporting and Monitoring

The site principal investigator is responsible for reporting any/all adverse events to the sponsor as described within the protocol. Refer to the adverse event and serious adverse event sections of the protocol for detailed information.

NOTE: Please see Appendix V for specific AE reporting regarding the study drug panitumumab for ACCRU personnel only.

ACCRU is responsible for notifying FDA and all participating investigators in a written safety report of any of the following:

- Any suspected adverse reaction that is both serious and unexpected.
- Any findings from laboratory animal or *in vitro* testing that suggest a significant risk for human subjects, including reports of mutagenicity, teratogenicity, or carcinogenicity.
- Any findings from epidemiological studies, pooled analysis of multiple studies, or clinical studies, whether or not conducted under an IND and whether or not conducted by the sponsor, that suggest a significant risk in humans exposed to the drug.
- Any clinically important increase in the rate of a serious suspected adverse reaction over the rate stated in the protocol or Investigator's Brochure (IB).

Definitions

Adverse Event

Any untoward medical occurrence associated with the use of a drug in humans, whether or not considered drug related.

The investigator is responsible for ensuring that all adverse events observed by the investigator or reported by the subject that occur after the first dose of investigational product(s)/study treatment through the safety follow-up visit are reported using the Event CRF.

Events Meeting the Adverse Event Definition

- Any abnormal laboratory test results (hematology, clinical chemistry, or urinalysis) or other safety assessments (eg, electrocardiogram, radiological scans, vital signs measurements), including those that worsen from baseline, that are considered clinically significant in the medical and scientific judgment of the investigator (ie, not related to progression of underlying disease).
- Exacerbation of a chronic or intermittent pre-existing condition including either an increase in frequency and/or intensity of the condition.
- New conditions detected or diagnosed after study treatment administration even though it may have been present before the start of the study.
- Signs, symptoms, or the clinical sequelae of a suspected drug-drug interaction.

Definition of Serious Adverse Event

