15.27 Known potential toxicities

Consult the package insert for the most current and complete information.

Serious Adverse Effects

Hepatotoxicity: [U.S. Boxed Warning]: Severe liver toxicity and hepatic failure (sometimes resulting in death) have been observed in clinical trials; hepatocyte necrosis with lymphocyte infiltration has been demonstrated with liver biopsy. Monitor hepatic function at baseline and during treatment. Interrupt therapy for hepatotoxicity; dose reductions or discontinuation are necessary depending on the severity and persistence.

Most Common Adverse Events, >10%:

Cardiovascular: Hypertension, hemorrhage

Central nervous system: Fatigue, dysphonia, pain, fever, headache.

Dermatologic: Skin toxicity, Palmar-plantar erythrodysesthesia, rash

Endocrine & metabolic: Hypocalcemia, hypophosphatemia, hyponatremia, hypokalemia

Gastrointestinal: Appetite decreased, lipase increased, diarrhea, mucositis, weight loss, amylase increased

Hematologic: Anemia, lymphopenia, thrombocytopenia, INR increased, neutropenia

Hepatic: AST increased, ALT increased, hyperbilirubinemia

Renal: Proteinuria

Miscellaneous: Infection, pain (including gastrointestinal and abdominal pain)

Less Common Adverse Events, 1% - 10%:

Hepatic: Hepatic failure

Rare Adverse Events (Important or life-threatening), <1%:

Gastrointestinal: Gastrointestinal perforation, gastrointestinal fistula,

Cardiovascular: Cardiac ischemia or infarction

Neurologic: Reversible posterior leukoencephalopathy syndrome (RPLS)

Dermatologic: Stevens-Johnson syndrome, toxic epidermal necrolysis

Additional risks:

Hypersensitivity reactions: Hypersensitivity reactions have been reported during post-approval use of regorafenib. Because these reactions are reported voluntarily from a population of uncertain size, it is not always possible to reliably estimate their frequency or establish a causal relationship to drug exposure

Wound Healing Complications: No formal studies of the effect of regorafenib on wound healing have been conducted. Since vascular endothelial growth factor receptor (VEGFR) inhibitors such as regorafenib can impair wound healing, discontinue treatment with regorafenib at least 2 weeks prior to scheduled surgery. The decision to resume regorafenib after surgery should be based on clinical judgment of adequate wound healing. Discontinue regorafenib in patients with wound dehiscence.

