16.54 Adverse Events

All eligible patients who have initiated treatment will be considered evaluable for adverse event analyses. The maximum grade for each type of adverse event will be recorded for each patient, and frequency tables will be reviewed to determine adverse event patterns. The overall adverse event rates for grade 3 or higher adverse events will be compared using Chi-Square or Fisher's Exact tests.

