18.1 Submission Timetable

Initial Material(s) -

CRF	Active-Monitoring Phase (Compliance with Test Schedule Section 4.0)
Institutional Contacts	
On-Study	
On-Study: Prior Systemic Therapy	
Adverse Events: Baseline	
RECIST Measurements: Baseline	≤2 weeks after registration
Laboratory Tests & Results: Baseline	
Supporting Documentation: Baseline ²	
Specimen Submission: Blood (Baseline) (see	

CRF	Active-Monitoring Phase (Compliance with Test Schedule Section 4.0)
Section 14.0)	
Specimen Submission: Tissue (Baseline) (see Section 17.0)	
Patient Status: Baseline	
Notice of New Primary ¹	
OP and Path Reports (see Section 17.0) ²	
Off Treatment	Submit ≤2 weeks after registration if withdrawal/refusal occurs prior to beginning protocol therapy
Patient Questionnaire Booklet-PRO/QOL: Linear Analogue Self Assessment (LASA)	≤ 2 weeks after registration - Patient questionnaire booklet must be used; copies are not acceptable for this submission.
PRO/QOL : Booklet Compliance ³	≤ 2 weeks after registration - This form must be completed only if the (name of booklet/s – or whatever verbiage you want to use to describe the booklet/s) contains absolutely NO patient provided assessment information.
ACCRU Deviation Form ¹	Submit only if applicable during all phases of the study (initial, active and observation)

1. Submit only if applicable.
2. Upload via the Supporting Documentation: Baseline form. COLOMATE Companion Trial Recommendation Form. This is in addition to the pathology material requirements for tissue submission (Section 17.0).
3. This form must be completed **only** if the Linear Analogue Self Assessment (LASA) contains absolutely NO patient provided assessment information.

Test Schedule Material(s)

CRF	Active-Monitoring Phase (Compliance with Test Schedule Section 4.0)	
	At each evaluation during treatment	At end of treatment (within 30 days after last dose of study drug)
Treatment (Intervention)	X	X
Treatment (Intervention): Dose Modifications, Omissions and Delays ¹	X	
Adverse Events: Solicited	X	X
Adverse Events: Other ¹	X	X
RECIST Measurements ²	X	X
Supporting Documentation ²	X	X
Laboratory Tests and Results	X	X
Specimen Submission: Blood (see Section 14.0)	X	
Patient Status: Treatment (Intervention)	X	X
Notice of New Primary ¹	X	X
Consent Withdrawal (choose appropriate form) ¹	X	X
• Consent Withdrawal: Specimen Only		

CRF	Active-Monitoring Phase (Compliance with Test Schedule Section 4.0)	

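### Section 16.54 analyses adverse event entries only and leaves the collected laboratory values unused, so laboratory harms may be under-reported, and magnesium is tested on treatment in Arm A only

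*Combined protocol and SAP*

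**What the plan says.** Goal 2.24 is to compare safety and tolerability between panitumumab rechallenge and standard therapy. The only planned analysis for it is section 16.54: "The maximum grade for each type of adverse event will be recorded for each patient", "frequency tables will be reviewed to determine adverse event patterns", and "The overall adverse event rates for grade 3 or higher adverse events will be compared" by a chi-square or Fisher's exact test. Under section 16.5 the p-values are descriptive.

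Laboratory data are collected in quantity. Section 4.0 schedules CBC and chemistry (including AST, ALT, bilirubin, calcium and potassium) in both arms before treatment, on Day 15, on Day 1 from cycle 2, and at end of treatment. The Day 15 visit may be dropped from cycle 7. Magnesium is measured at screening in everyone, but footnote 5 restricts the on-treatment and end-of-treatment tests: "Only for patients receiving panitumumab". Section 18.1 has a "Laboratory Tests and Results" form due at each evaluation and at end of treatment.

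Section 10.0 lists, among events that meet the adverse event definition, abnormal laboratory results "that are considered clinically significant in the medical and scientific judgment of the investigator (ie, not related to progression of underlying disease". Section 10.53 asks for grade 2 events at least possibly related to treatment, and section 10.532 for all grade 3 and 4 events whatever their attribution. The three solicited terms in section 10.52 are fatigue, diarrhea and acneiform rash; none is a laboratory term.

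**The concern.** Several of the main listed harms are laboratory findings, and they differ by drug. For regorafenib, section 15.27 carries a boxed warning ("Severe liver toxicity and hepatic failure (sometimes resulting in death) have been observed in clinical trials") and lists AST, ALT and bilirubin increases above 10%. TAS-102 has anemia, neutropenia and thrombocytopenia (15.37). Panitumumab has hypomagnesemia and hypokalemia (15.17).

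The plan reaches these harms only through adverse event entries. Whether an abnormal value becomes an entry depends partly on a judgement about clinical significance and progression. That judgement is hard to make for liver tests in patients with liver metastases. No blinding is described: Arm A is an infusion and Arm B an oral drug chosen by the physician. If investigators apply the judgement differently to the two arms, the comparison for goal 2.24 reflects reporting as well as toxicity. The values that could check this are submitted, but no analysis uses them.

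**Working it through.** The documents state no figure on this point, so there is none to reproduce. The check has three steps.

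**1. Where a laboratory value can be lost on its way to 16.54**

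- Grade 1: not requested by 10.53 and not solicited in 10.52, so generally absent from the analysis.
- Grade 2 judged unrelated: not requested by 10.53.
- Grade 2 judged related, and grade 3 or 4: requested, but only once the value counts as an adverse event. The section 10.0 judgement comes before that. A rise in ALT attributed to liver progression could be left out before 10.532 applies.
- Combined liver signal: footnote a of section 8.2 names "Any occurrence of AST or ALT more than 3 times ULN with concurrent bilirubin more than 2 times ULN". No analysis counts how many patients met it.
- Baseline level: section 3.19c admits AST and ALT up to 5 x ULN with liver involvement. A maximum grade alone cannot separate a rise present at entry from worsening on treatment.

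**2. What incomplete entry would do (assumed inputs)**

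Observed rate = true rate x share of events entered. Take 53 patients per arm (section 16.15). The true rates and shares are assumptions. Rejection is the exact probability that a two-sided Fisher test gives p ≤ 0.05, from enumerating two binomials.

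| True grade 3+ laboratory rate, A / B | Share entered, A / B | Observed, A / B | Rejection |
|---|---|---|---|
| 15% / 15% | 100% / 100% | 15% / 15% | 2.6% |
| 15% / 15% | 90% / 60% | 13.5% / 9% | 5.8% |
| 20% / 20% | 100% / 100% | 20% / 20% | 3.0% |
| 20% / 20% | 90% / 70% | 18% / 14% | 5.1% |
| 20% / 20% | 100% / 50% | 20% / 10% | 21.4% |
| 10% / 35% | 100% / 100% | 10% / 35% | 84.8% |
| 10% / 35% | 70% / 70% | 7% / 24.5% | 62.4% |
| 10% / 35% | 90% / 70% | 9% / 24.5% | 48.4% |
| 10% / 35% | 70% / 90% | 7% / 31.5% | 88.0% |

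Modest differences in entry shift the rates by a few points. In the 15% case, 0.135 x 53 is about 7 patients and 0.09 x 53 about 5; 7 versus 5 gives Fisher p = 0.76. Only a large gap such as 100% versus 50% makes equal toxicity look clearly different. Even equal under-entry (70% / 70%) costs the chance of seeing a true difference. The last two rows show that the error can go either way.

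These rates concern laboratory events alone. If 16.54 counts patients with any grade 3+ event, the effect is diluted, because a patient with another grade 3+ event is counted anyway.

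**3. Magnesium**

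This is a different mechanism. With on-treatment tests scheduled in Arm A only, an Arm B case appears only if a site tests on its own initiative. If 16.54 counts patients with any grade 3+ event, each Arm A patient whose sole such event is hypomagnesemia adds 1/53 = 1.9 percentage points to that arm. Grading the collected values cannot supply tests that were not drawn in Arm B.

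**The case against.** The strongest case against has five parts.

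- Section 10.532 requires grade 3 and 4 events regardless of attribution, and 10.1 grades them by CTCAE v5.0. The dose-modification tables in 8.2 and 8.3 list liver-test, neutrophil and platelet changes as adverse events, and 10.31 uses several laboratory terms the same way. A value that prompts a dose hold is hard to call clinically insignificant. This stands, and it makes substantial loss at grade 3+ less likely than at lower grades. It does not remove the earlier judgement in section 10.0.
- The list in section 10.0 sits under a broad definition, and the list of events that do not qualify never mentions laboratory values. Reading the criterion as exclusive is an inference. This stands: the text permits the filter and does not clearly impose it. Sites may therefore differ.
- The capture rates above are invented, and secondary p-values are already descriptive. Both stand.
- A raw count of the combined liver criterion would include patients who met its transaminase half at entry. The criterion is also specific to regorafenib, in a section marked as suggested and not mandated. Both stand, and the fix below is built around them.
- The DSMB reviews safety at least twice a year. That protects patients during the trial; it does not supply the comparison in goal 2.24.

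A reader might infer that laboratory harms are in fact under-reported, and unevenly so. The documents do not support that: they give no capture rate and nothing that fixes the direction.

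**Conclusion.** The point holds as a risk and as an avoidable gap. The plan submits laboratory values at each evaluation and analyses none of them. Its safety comparison rests on entries that may pass through a judgement made with the arm known, so laboratory harms may be under-reported, possibly differently by arm. The loss is probably clearest for grade 1 and unrelated grade 2. For grade 3+ it is possible but limited by 10.532. Its size cannot be estimated from the documents; the illustrations run from a few percentage points to a halving of one arm's rate, depending wholly on assumed capture.

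The magnesium asymmetry is firmer, because it follows from the schedule itself. It would tend to add hypomagnesemia to Arm A's count; by how much is not known.

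The primary analysis is unaffected. This is an inexpensive improvement to a descriptive secondary analysis, and not a flaw that undermines the trial.

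**What to change.** Add to section 16.54:

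- Derive CTCAE v5.0 grades from the submitted laboratory values. Tabulate worst post-baseline grade and shift from baseline by arm, and by drug within Arm B, for AST, ALT, bilirubin, neutrophils, platelets, hemoglobin, calcium and potassium.
- Count patients who newly meet AST or ALT above 3 x ULN with concurrent bilirubin above 2 x ULN, shown by baseline transaminase level and liver involvement. This is a descriptive count and not a treatment rule.
- Summarise magnesium in Arm A only, and state that the schedule does not allow a comparison between arms.
- Report the grade 3+ adverse event comparison with and without hypomagnesemia.

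Results stay descriptive under 16.5. The cost is a few sentences and routine programming, with no new tests. The tables gain rows, some of which will reflect progression in the liver. The change assumes that the laboratory form holds the analytes listed in section 4.0; its fields are not shown, so this should be confirmed first.

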Appendix IV(A) – Patient Medication Diary: Regorafenib

Appendix IV(B) – Patient Medication Diary: TAS-102

Appendix V – Submission of Safety Data Regarding the Study Drug Panitumumab

Schema

NOTE: Patients must be registered to ACCRU-GI-1611(COLOMATE) and have received the COLOMATE Companion Trial Recommendation Form prior to being registered on this study.

*Cycle length = 28 days

*Treat until progression or maximum of 24 cycles

Generic name: Panitumumab Brand name(s): Vectibix Availability: Amgen	Generic name: TAS-102 Brand name(s): TAS-102 Trifluridine FTD)/ Tipiracil (TPI) (TAS-102, Lonsurf®) Availability: Commercial
Generic name: Regorafenib Brand name(s): Stivarga Availability: Commercial	

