1.3 Blood-based molecular profiling to Identify Patients for EGFR Antibody Rechallenge

Several recent studies have demonstrated that molecular profiling of cell free DNA (cfDNA) could be useful for identifying patient sub-populations most likely to benefit from EGFR antibody rechallenge. As part of an investigator-initiated trial at Duke University (NCT02008383), comprehensive blood-based genomic profiling was performed on patients with EGFR-refractory, *RAS* wild-type metastatic CRC. This profiling effort utilized the Guardant360™ assay (Guardant Health, Redwood City, CA), a >70-gene NGS-based blood test. Among the 69 patients with EGFR-refractory disease who received blood-based genomic profiling, 18 patients (26%) had no detectable resistance-conferring mutation or amplification [35].

Recent studies have further shown that cfDNA profiling is an effective diagnostic tool to identify patients likely to benefit from EGFR antibody rechallenge. In a single-arm phase II study conducted in Italy (CRICKET), 28 patients with *RAS* wild-type metastatic CRC who received first-line FOLFIRI/cetuximab and second line FOLFOX/bevacizumab were assigned to third line irinotecan/cetuximab [36]. Six patients (21.5%) experienced partial response, with a median PFS of 3.4 months and a median overall survival (OS) of 9.8 months. Utilizing droplet digital (dd) PCR, 12 patients had a baseline *RAS* mutation detected in blood, and 13 patients had no baseline *RAS* mutation detected. The response rate for patients who were *RAS* wild-type in blood was 38%, with a median PFS of 4.0 months and a median survival of 12.5 months. The use of cfDNA to identify patients likely to benefit from EGFR antibody rechallenge is further supported by results of a phase II randomized trial comparing the novel EGFR antibody admixture SYM004 versus investigator choice (IC) therapy in patients with EGFR refractory metastatic CRC [37]. In the intent-to-treat (ITT) population, there was no survival benefit for SYM004 compared to IC. However, a retrospective analysis of patients who were *RAS/BRAF/EGFR* mutation negative in blood found improved survival in patients treated with SYM004 compared with IC (median OS, 12.8 and 7.3 months, respectively).

Collectively, these results support the potential clinical benefit of EGFR antibody rechallenge, and suggest that cfDNA profiling may identify patients most likely to benefit.

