8.0 Dosage Modification Based on Adverse Events

Subjects will be monitored continuously for AEs from the date of first dose of study drug and for 30 days after the last dose of study drug. Subjects will be instructed to notify their treating physician of any and all AEs. All AEs should also be managed with supportive care at the earliest signs of toxicity. Subjects should receive appropriate supportive care measures as deemed necessary by the Investigator. Suggested supportive care measures for the management of adverse events are outlined in Section 9.0.

Subjects experiencing one or more AEs due to study drug(s) may require dose modification(s) as described in Sections 8.1, 8.2, and 8.3. If multiple adverse events are seen, administer dose based on greatest reduction required for any single adverse event observed. Reductions or increases apply to treatment given in the preceding cycle and are based on adverse events observed since the prior dose. At the discretion of the Investigator, dose modifications are permitted outside of those provided in the protocol if the Investigator feels it is in the interest of the subject's safety (e.g., due to multiple toxicities, persistent toxicities, intercurrent illness, or short term compliance or monitoring issues, etc.). Subjects may need to be followed at least weekly when the study drug is held for clinically significant toxicity until the toxicity returns to Grade ≤ 1 or is determined to be controlled, chronic, or irreversible.

Dosing interruptions are permitted in the case of medical / surgical events or logistical reasons not related to study therapy (e.g., elective surgery, unrelated medical events, patient vacation, and/or holidays). Subjects should be placed back on study therapy within 4 weeks of the scheduled interruption, unless otherwise discussed with the Lead PI. The reason for interruption should be documented in the patient's study record.

ALERT: ADR reporting may be required for some adverse events (See Section 10)

8.1 Panitumumab: This section applies to adverse events associated with panitumumab. For adverse events associated with regorafenib, please refer to Section 8.2 and for TAS-102, please refer to Section 8.3.

* Located at [REDACTED]

** Use the following to describe actions in the Action column:

- Omit = Treatment is not given for this cycle
- Hold/Delay = Treatment can be made up as part of this cycle
- Discontinue = Treatment is totally stopped

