16.0 Statistical Considerations and Methodology

16.1 Overview and Study Design

This is a randomized Phase II study which is designed to compare the overall survival (OS) in patients with EGFR refractory *RAS* wild-type metastatic CRC, who are randomized to panitumumab or standard therapy (TAS-102 or regorafenib). Prior studies have shown that the median OS is around 6.5 months for patients in this disease population receiving TAS-102 or regorafenib and PFS is around 1.9 months for patients receiving TAS-102 or regorafenib in this disease population [40, 41]. It is hypothesized that panitumumab can increase the median OS to at least 10 months. In addition to OS, this trial will also compare the overall response rate, PFS, adverse event rates, and self-reported quality of life outcomes (measured by LASA) between the panitumumab arm and standard therapy (TAS-102 or regorafenib).

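### Grade 3+ adverse events are compared as crude proportions over an observation window that lengthens with time on treatment; a common-window comparison and a patient-month rate should be added

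*Combined protocol and SAP*

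**What the plan says.** Goal 2.24 is a between-arm comparison of safety and tolerability. Section 16.54 carries it out as follows: "The overall adverse event rates for grade 3 or higher adverse events will be compared using Chi-Square" or Fisher's exact tests. The unit is the patient's worst grade: "The maximum grade for each type of adverse event will be recorded for each patient". The analysis set is defined so: "All eligible patients who have initiated treatment will be considered evaluable for adverse event analyses".

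The length of observation is set elsewhere. Section 8.0: "Subjects will be monitored continuously for AEs from the date of first dose of study drug and for 30 days after the last dose". The Schema: "Treat until progression or maximum of 24 cycles", with 28-day cycles, in both arms.

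On how long that may be, Section 16.1 covers control only: "PFS is around 1.9 months for patients receiving TAS-102 or regorafenib". No PFS or treatment duration is stated for panitumumab. Section 1.3 cites an irinotecan/cetuximab rechallenge study with median PFS of 3.4 months overall and, in the 13 patients who were RAS wild-type in blood, results "with a median PFS of 4.0 months and a median survival of 12.5 months". Section 1.1 cites a non-randomized cetuximab rechallenge study (n=39) with median PFS of 6.6 months.

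The introduction to Section 16.5 makes all secondary-endpoint p-values descriptive. Section 16 contains no rate per unit of exposure, no time-to-first-event analysis and no fixed common window for adverse events.

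**The concern.** A test on whether a patient ever had a Grade 3+ event treats all patients as if they had been watched equally long. Here the watching time is treatment time plus 30 days, and treatment time ends largely with progression. The comparison therefore mixes toxicity with efficacy: the arm that keeps patients on treatment longer collects more events even when its monthly toxicity is the same. If panitumumab does what the trial hopes, the safety table would lean against it, and a reader could not separate greater toxicity from longer exposure.

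**Working it through.** **The plan's own figure.** There is none for this comparison: no adverse event rate, alpha, power or panitumumab treatment duration is given.

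**Inputs from the documents.** Control median PFS 1.9 months (16.1); cited rechallenge medians 3.4 and 4.0 (1.3) and 6.6 months (1.1); OS hazard ratio 0.65 and 53 evaluable patients per arm (16.15); follow-up of 30 days after last dose (8.0).

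**Assumptions.** Time on treatment is exponential with median equal to PFS. The 30 days count as 1 month. The hazard L of a first Grade 3+ event is the same in both arms. The test level is two-sided 0.05. The documents give none of these. The 24-cycle cap (22 months) changes the results by less than one percentage point.

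**Step 1: mean observation time** = median/ln 2 + 1.
- Control: 1.9/0.693 + 1 = 3.74 months.
- Panitumumab at 3.4, 4.0 and 6.6: 5.91, 6.77 and 10.52 months, ratios 1.58, 1.81 and 2.81.
- If the OS hazard ratio of 0.65 is assumed to hold for PFS: median 1.9/0.65 = 2.92, mean 5.22 months, ratio 1.40.

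**Step 2: proportion affected under a constant hazard.** With mu = ln 2/median, P = 1 - exp(-L) × mu/(mu + L). Take L = 0.10 per month.
- Control: mu = 0.365; P = 1 - 0.905 × 0.365/0.465 = 0.290.
- Panitumumab at 4.0: mu = 0.173; P = 1 - 0.905 × 0.173/0.273 = 0.426.

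Rejection rates against panitumumab come from exact enumeration of all outcomes with 53 per arm. The nominal rate in that one direction is 2.5%.

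| Panitumumab median (months) | Control | Panitumumab | Chi-square rejects | Fisher rejects |
|---|---|---|---|---|
| 3.4 | 29% | 39% | 21% | 15% |
| 4.0 | 29% | 43% | 32% | 25% |
| 6.6 | 29% | 54% | 74% | 68% |

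With L between 0.05 and 0.20, chi-square rejection at median 4.0 is 24-32%. At median 2.92 it is about 10-13%.

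**Step 3: the same check with early toxicity.** If the hazard acts only in the first W months (W > 1), P = 1 - exp(-L) × [mu/(mu + L) × (1 - e) + e], where e = exp(-(mu + L)(W - 1)).
- W = 3, L = 0.15: control 30%; panitumumab 32%, 33% and 34% at medians 3.4, 4.0 and 6.6. Chi-square rejects against panitumumab in about 5%, 5% and 7%.
- Events only in month 1: every patient is observed for at least 30 days, so the arms have equal proportions and there is no bias.

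**Step 4: the remedy under the Step 2 model.** Restricting to the first 56 days (1.84 months) gives 15.8% on control against 16.3% (median 4.0) or 16.5% (median 6.6), with false rejection against panitumumab of about 3%. The patient-month rate ratio is 1.00 by construction when the hazards are equal and constant.

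**The case against.** Several counter-arguments have force.

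- **Panitumumab's treatment time is unknown.** A reader might infer that the plan expects panitumumab patients to be observed about twice as long. It does not say so. The cited figures come from small cetuximab studies, one with added irinotecan, and PFS is only a proxy, because patients also stop for toxicity or choose another therapy (Section 13). This stands: the ratio is a range from about 1.4 to 2.8, not a design figure.
- **The size depends on the hazard shape.** A reader might take the 74% as the expected false-alarm rate. It needs the longest cited PFS, a constant hazard and the uncorrected chi-square. With early toxicity the bias is a few points or none. This stands, but the plan does not say which pattern it expects, and the crude table cannot show it.
- **Nothing turns on the test.** The p-values are descriptive, the final decision rests on OS (16.13, 16.14), and the suspension rule in 16.4.2 looks at each arm separately. This stands and limits the severity. It does not repair the crude percentages, which carry the same dependence on exposure.
- **Cumulative incidence is a legitimate measure.** The share of patients ever affected under each strategy is meaningful, and goal 2.24 does not ask for toxicity per month. A reader might infer that the crude table is an error; it is not. The gap is that it is the only comparison planned.
- **Onset dates may not exist.** Footnote 1 of the Test Schedule asks only for maximum grade at data entry. However, Section 18.1 has adverse event forms submitted at each evaluation, so first occurrence can at least be placed by evaluation.

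Section 10.54 also has late events reported during survival follow-up, so the 30-day limit is not the end of all reporting.

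**Conclusion.** The point holds as a conditional one. Section 16.54 plans only a crude comparison, and observation time is tied to time on treatment. If panitumumab delays progression, equal monthly toxicity gives a higher panitumumab proportion. The excess is 10 to 25 percentage points under a constant hazard of 0.10 per month and the cited PFS range, 2 to 4 points if toxicity ends by month 3, and zero if it is confined to month 1. These sizes rest on PFS as a stand-in for treatment time, on exponential durations and on an assumed hazard. The documents do not support treating any one of them as the expected result, or saying that a trial decision is affected. The harm is to how the safety comparison would be read. It is worth correcting because the change is cheap.

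**What to change.** In Section 16.54, keep the crude Grade 3+ table and label it as cumulative incidence over the treatment-dependent window. Add:

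1. The Chi-Square or Fisher comparison restricted to a common window, the first 2 cycles (56 days from first dose).
2. First Grade 3+ events per patient-month at risk (first dose to 30 days after last dose, ending at the first event or death), with rate ratio and confidence interval. Where onset dates are not captured, use the evaluation or cycle of first occurrence.
3. Treatment duration by arm.

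The cost is a paragraph of analysis text, one extra table and a check of what the adverse event forms record. Treatment, sample size and the primary analysis are unchanged. The rate in item 2 assumes a roughly constant hazard, and item 1 does not cover later toxicity, so the two should be read together.
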